4.1.1.2 Presentation

The purpose of this presentation is to provide an overview of the patient flow in the study, i.e., how many patients entered the respective study phases, how many completed the respective phases, the reasons for discontinuing a phase etc.

The tabulation will include the number, and percentage, of subjects falling into different disposition categories, i.e., it will be a descriptive summary in accordance with the rules described in Section 3.3. It will, for instance, include the following categories: subjects enrolled, subjects entering each of the phases, subjects discontinuing each of the phases, as well as reason for discontinuation, subjects completing and discontinuing treatment in the maintenance phase.

Effect of COVID-19 on the disposition

Subjects whose disposition status was affected by COVID-19 will be presented separately, the presentation including the number, and percentage, of subject who discontinued treatment and / or study due to COVID-19. An overview of subjects whose study conduct was affected by COVID-19, e.g., whose visits were impacted and were performed remotely rather than on site, will also be provided.

Recruitment

The recruitment pattern, in terms of the number, and percentage, of subjects per region, country and site, will be provided. This will be described in terms of subjects Screened, Randomized, and Dosed.

4.1.2 Analysis Sets

4.1.2.1 Definitions and Derivations

There will be five separate analysis sets in the study. For the definition, see Section 3.2. Explicitly, the FAS set will consist of all patients receiving a randomization number, while the different SAS sets will be determined by whether a patient has at least one dose of SZC provided to them, as per the drug accountability module in the eCRF, during the respective phases of the study.

4.1.2.2 Presentation

The analysis sets will be described descriptively, with the number of subjects in each set displayed by treatment arm, along with the overall total consisting of both treatment arms. In addition, the number of subjects excluded from each analysis set, along with the reason for exclusion, will be displayed in the same manner.

4.1.3 Protocol Deviations

4.1.3.1 Definitions and Derivations

All protocol deviations will be recorded and stored in Veeva Vault (a component of the unified platform for clinical trial management, that incorporates e.g., the electronic trial master file and the clinical trial management system), regardless of their detection method. The data set containing the PDs will then be exported from this system at the time of the database lock, to be converted into a SAS data set and included in the data base for the purpose of analysis and reporting.

4.1.3.2 Presentation

Important protocol deviations will be summarised descriptively in accordance with the rules described in Section 3.3.

The number of patients with at least one protocol deviation will be presented, and specific protocol deviations will be presented and nested within this. Subjects may have more than one protocol deviation.

Subjects with protocol deviations relating to COVID-19 will be presented in the same format as described above.

4.1.4 Demographics

4.1.4.1 Definitions and Derivations

Demographic data will be collected in the eCRF during screening. The variables collected, and summarised, are:

- Age (in years and by age category (18 - <65, \geq 65 - <85, \geq 85 years))
- Sex (Male, Female)
- Ethnicity (Hispanic or Latino, Not Hispanic or Latino)
- Race (White, Black or African American, Asian, American Indian or Alaska Native, Native Hawaiian or other Pacific Islander, Other)
- Country
- Geographic Region (Asia, Europe, North America, South America)

Age group will be derived using the continuous age variable collected in the eCRF. Geographic region will be derived from country.

4.1.4.2 Presentation

The demographic characteristics will be summarised descriptively in accordance with the rules set out in Section 3.3.

4.1.5 Baseline Characteristics

4.1.5.1 Definitions and Derivations

The baseline characteristics that will be summarised include:

- Height (cm)
- Weight (kg)
- Body Mass Index (BMI) (kg/m²)

The BMI will be derived for each subject by calculating $\{\text{weight at screening (kg)}\}/\{\text{height (m)}\}^2$.

4.1.5.2 Presentation

Baseline characteristics will be summarised descriptively and presented according to the rules described in Section 3.3.

4.1.6.2 Presentation

Disease characteristics will be summarised descriptively and presented according to the rules described in Section 3.3.

In addition, a cross-tabulation of the eGFR and the UACR categories, as described above, will be created, the tabulation including the number and percentage of patients in each eGFR / UACR category. For the percentage calculation, the number of patients SAS-IP will be used as the denominator.

4.1.7 Medical History and Concomitant Disease

4.1.7.1 Definitions and Derivations

Only specific medical history will be collected in the eCRF (i.e., corresponding to specific terms). It will be classified in terms of preferred term (PT) and system organ class (SOC).

This will be done according the latest MedDRA version the time of database lock. The definition of medical history will not distinguish between prior and ongoing medical history.

4.1.7.2 Presentation

Medical history will be summarised descriptively and presented according to the rules described in Section 3.3.

Subjects will only be counted once per SOC and PT, regardless of the number of occurrences within each category. PT will be nested within the appropriate SOC and sorted by international order of SOC and alphabetically for PT.

4.1.8 Concomitant Medications

4.1.8.1 Definitions and Derivations

Concomitant medications, including medications taken during the screening period, will be collected in the eCRF and classified by ATC classification and generic term.

Baseline medications for a particular phase are defined as medications with a start date no later than the beginning of the phase in question, and a stop date after the beginning of the phase (or ongoing at the end of study).

Concomitant medications for a particular phase are defined as medications which a patient takes during that phase. Explicitly, it is medications with a start date earlier than the end of the specific phase and a stop date during or after the same phase (or ongoing at the end of study). Missing start and stop dates will be handled as set out in Section 3.3.1.2.

A rescue medication is defined as a medication used in connection to the adverse event of severe hyperkalaemia requiring rescue as determined by the investigator.

Two types of medications are considered to be disallowed in the study:

- **A potassium binder is disallowed** if it is not a short term (≤ 2 days) rescue medication. Potassium binders are defined by the following ATC codes / ingredients:

Table 1: Disallowed potassium binders

| ATC code | Ingredients |
|----------|-------------------------------|
| V03AE | SODIUM POLYSTYRENE SULFONATE |
| V03AE | CALCIUM POLYSTYRENE SULFONATE |
| V03AE | PATIROMER |
| V03AE | PATIROMER CALCIUM |
| V03AE | PATIROMER SORBITEX CALCIUM |

- **RAASi medication is disallowed** if it is taken concomitantly with Valsartan or Lisinopril, after the initiation phase, as specified by the CSP.

4.1.8.2 Presentation

Concomitant medications will be summarised descriptively and presented according to the rules in Section 3.3. Disallowed medications and baseline RAASi medications will be summarised in a similar manner.

Medications will be summarised according to ATC classification and then by drug name within each classification. Further, the number of subjects on any medication will also be presented.

4.1.9 Study Drug Exposure and Compliance

4.1.9.1 Definitions and Derivations

Study periods definition for exposure and compliance

Duration of exposure will be defined separately for each of the study periods. Exposure will be evaluated both for RAASi and SZC/Placebo (SZC alone for the initiation and the run-in phases).

Total exposure to study drug within a period will be defined as total prescribed time on IP (i.e. the days between the first and the last scheduled dose, inclusive) during that period.

The duration of exposure (months) will be calculated separately for exposure to SZC/placebo and Lisinopril/valsartan.

Exposure excluding interruptions to the study drug will be defined as the number of days a subject was scheduled to be on IP, during the respective periods, excluding any scheduled dose interruptions (i.e., as assigned by the investigator).

Duration of exposure to a particular dose will be defined as the time the dose was prescribed, excluding interruptions.

Compliance to SZC/Placebo will not be presented, neither summarised, nor listed.

Compliance to IP RAASi (lisinopril, valsartan, irbesartan) will not be presented either, neither summarised, nor listed.

4.1.9.2 Presentation

Exposure, total and excluding interruptions will be summarised descriptively and presented according to the rules described in Section 3.3. Duration of exposure to a particular dose level will be summarised in a similar manner, by treatment group and dose level, for each combination of study drug and study period.

Discrete summaries of the number and percentage of patients receiving a particular dose level of SZC/Placebo and lisinopril/valsartan (including dose 0, which would correspond to a temporary, or a permanent, interruption) will be presented for the start of the run-in phase, end of the run-in phase and every 3 months during the maintenance phase.

The mean dose will be plotted over time (per day), for both SZC/Placebo and Lisinopril/valsartan.

4.2 Endpoint Analyses

This section covers details related to the analyses of primary, secondary, and other endpoints, including sensitivity and supportive analyses.

All the efficacy analyses will be aimed at evaluating the potential effect of SZC during the randomized treatment phase of the study (i.e., the maintenance phase). As such, the estimands for these analyses can be described as follows.

Population: For all of the efficacy analyses specified in the Table 2 below, the population, in estimand terminology, consists of the patients satisfying the randomization criteria of the study. That is, patients who satisfy the inclusion and exclusion criteria at study entry, and who achieve, and maintain, normokalaemia after the initiation and the run-in phases.

Treatment: For all the analyses performed on the maintenance phase, the treatment, in the estimand framework, is SZC and placebo while receiving lisinopril/valsartan, as guided by the CSP. For all the comparisons of SZC vs Placebo, the Placebo group will be used as the reference.

Intercurrent events: The following intercurrent events that might have impact on the interpretation or existence of the measurements associated with the clinical question have been identified:

- Death
- Permanent discontinuation of SZC/Placebo
- Initiation of long-term potassium-lowering treatment

- Introduction of a concomitant medication that may directly affect CKD progression (e.g., SGLT2 inhibitors)
- Onset of ESKD (the definition of which can be found in CSP section 8.1.2 and includes initiation of dialysis or a kidney transplant)
- Change in IP dosage (SZC or RAASi)

It may be hypothesized that a change in IP dosage (SZC or RAASi) may cause an acute haemodynamic effect that, although visible in the eGFR profile, might not reflect a true change in CKD progression but only a temporary change in eGFR. A set of analyses aimed at further evaluating the presence, and potential impact, of such effects will be performed, see Section 4.2.7 for details.

The main strategy for handling the intercurrent events in the analysis of the primary objective will be that of treatment policy. That is, the intercurrent events that lead to a potential change in the measurements profile, but for which post-intercurrent event data are available (e.g. treatment discontinuation, introduction of eGFR altering concomitant therapy), will be ignored in the analysis, and all data obtained, both pre and post the intercurrent event, will be included as planned. In the table below, the approach for handling intercurrent events described above is referred to as “main strategy”. The exception to this rule will be the events for which it could be argued that, after experiencing these, a participant ceases to belong to the population of interest. For such an event, any data collected post event occurrence will be excluded from the main analyses. Onset of ESKD is the only type of event currently identified in this category.

In addition to the main analyses, a number of supplementary analyses of the primary and secondary endpoints, utilizing a hypothetical intercurrent event strategy, will be carried out. In this case, data from after the intercurrent events that lead to a potential change in the measurements profile will not be used in the analysis. Instead, a hypothetical scenario that the intercurrent event did not have occur will be considered. For example, for the intercurrent event of long-term potassium lowering treatment and a hypothetical strategy, it will correspond to a hypothetical situation where such treatment is not available to participants. An equivalent situation will apply to the remaining hypothetical intercurrent events.

Missing data: If not otherwise specified, no imputation of missing data will be performed. Rather, missing data will be handled indirectly through e.g., application of models for longitudinal data, such as regressions with random effects, and survival analysis approaches. The same applies for missing covariate data used in the sub-group analyses: no imputation will be performed.

One exception to this rule will be the eGFR measurements obtained as re-tests, if, due to operational reasons such as unavailability of kits, the planned eGFR samples could not be taken at a scheduled visit (see Section 4.2.1). Such measurements may be used in the eGFR-based analyses.

Covariates: For each of the model-based analyses detailed below, the following variables are included as covariates in the model:

- Treatment (SZC vs Placebo).
- Geographic region.
- Hyperkalaemia at the beginning of the initiation phase (yes/no), as indicated by the strata applied at randomisation.
- Use of SGLT2i/Finerenone at randomisation (yes/no), as indicated by the concomitant-medications collection.
- Age.

Further covariates may be added as appropriate, and these will be specified in the descriptions below.

Table 2: Overview of the main and the supplementary analyses

|

| Statistical category | Endpoint | Intercurrent event strategy | Population level summary | Details in section |
|--|---|--|--|--------------------|
| Primary | | | | |
| Primary objective #1: To determine if treatment with S2C, as adjunct to ACEi/ARB therapy (lisinopril or valsartan), is superior to placebo in slowing CKD progression, assessed as the reduction in participant's expected eGFR decline over time | | | | |
| Main | Total slope: eGFR measurements starting at randomisation (up to visit 17/week 69) | Main strategy | Difference in mean total eGFR slopes | 4.2.1.1 |
| | Chronic slope: eGFR measurements, starting at 12 weeks after randomisation (up to visit 17/week 69) | Main strategy | Difference in mean chronic eGFR slopes | 4.2.1.1 |
| Supplementary | Total slope: eGFR measurements starting at randomisation (up to visit 17/week 69) | Hypothetical strategy wrt initiation of long-term potassium lowering treatment and initiation of potentially eGFR altering treatment | Difference in mean total eGFR slopes | 4.2.1.2 |
| | Chronic slope: eGFR measurements, starting at 12 weeks after randomisation (up to visit 17/week 69) | Hypothetical strategy wrt initiation of long-term potassium lowering treatment and initiation of potentially eGFR altering treatment | Difference in mean chronic eGFR slopes | 4.2.1.2 |

| Statistical category | Endpoint | Intercurrent event strategy | Population level summary | Details in section |
|----------------------|----------|-----------------------------|--------------------------|--------------------|
| Secondary | | | | |
| | | | | |

Secondary objective #1: To determine if treatment with SZC, as adjunct to ACEi/ARB therapy (lisinopril or valsartan), is superior to placebo in reducing the incidence of the composite of kidney failure outcomes comprising: sustained $\geq 40\%$ decline in eGFR, onset of ESKD, and death from kidney failure

| Statistical category | Endpoint | Intercurrent event strategy | Population level summary | Details in section |
|----------------------|---|-----------------------------|--------------------------|---|
| Supplementary | Time from randomisation to the first occurrence of any component in the composite of 
 - Sustained $\geq 50\%$ decline in eGFR - Onset of ESKD (kidney transplantation, maintenance dialysis, or sustained low eGFR) - Death from kidney failure | Main strategy | Hazard ratio | 4.2.2.2 |
| | | | | Secondary objective #2: To determine if treatment with SZC, as adjunct to ACEi/ARB therapy (lisinopril or valsartan), is superior to placebo in reducing the incidence of lisinopril/valsartan dose decrease, in participants on lisinopril/valsartan at randomisation |
| Main | Time from randomisation to first lisinopril/valsartan dose decrease | Main strategy | Hazard ratio | 4.2.3 |
| | | | | Secondary objective #3: To determine if treatment with SZC, as adjunct to ACEi/ARB therapy (lisinopril or valsartan), is superior to placebo in reducing albuminuria |
| Main | UACR measurements at scheduled visit 13 | Main strategy | Difference in means | 4.2.4.1 |

| Statistical category | Endpoint | Intercurrent event strategy | Population level summary | Details in section |
|--|--|-----------------------------|--|--------------------|
| Supplementary | Logarithm of the ratio between UACR at visit 13 and baseline (pre-randomization) UACR | Main strategy | Ratio of medians of percent change from baseline | 4.2.4.2 |
| Secondary objective #4: To determine if treatment with SZC, as adjunct to ACEi/ARB therapy (lisinopril or valsartan), is superior to placebo in increasing serum bicarbonate levels | | | | |
| Main | Serum bicarbonate measurements at scheduled visits after randomisation (up to visit 17/week 69) | Main strategy | Difference in means, overall (across visits) | 4.2.5.1 |
| Supplementary | Serum bicarbonate measurements at scheduled visits after randomisation (up to visit 17/week 69) | Main strategy | Difference in means, at each visit | 4.2.5.2 |
| Supplementary | Serum bicarbonate classification: normal ($> 22.0 \text{ mmol/L}$) or non-normal ($\leq 22.0 \text{ mmol/L}$) at scheduled visits after randomisation (up to visit 17/week 69) | Main strategy | Difference in probabilities, at each visit | 4.2.5.2 |

| Statistical category | Endpoint | Intercurrent event strategy | Population level summary | Details in section |
|---|--|-----------------------------|--|--------------------|
| Secondary objective #5: To determine if treatment with S7C, as adjunct to ACEi/ARB therapy (lisinopril or valsartan), is superior to placebo on maintenance of normokalaemia | | | | |
| Main | S-K level classification; normal (3.5-5.0 mmol/L) or non-normal (< 3.5 or > 5.0 mmol/L) at scheduled visits after randomisation (up to visit 17/week 69) | Main strategy | Odds ratio, overall (across visits) | 4.2.6.1 |
| Supplementary | S-K level classification; normal (3.5-5.0 mmol/L) or non-normal (< 3.5 or > 5.0 mmol/L) at scheduled visits after randomisation (up to visit 17/week 69) | Main strategy | Odds ratio, at each visit | 4.2.6.2 |
| Supplementary | S-K level classification; normal (3.5-5.0 mmol/L) or non-normal (< 3.5 or > 5.0 mmol/L) at scheduled visits after randomisation (up to visit 17/week 69) | Main strategy | Difference in probabilities, at each visit | 4.2.6.2 |

Note: In case of a local market valsartan shortage, ibdesartan will be temporarily used instead.

4.2.1 Analyses of Primary objectives

Primary objective #1: *To determine if treatment with SZC, as adjunct to ACEi/ARB therapy (lisinopril or valsartan), is superior to placebo in slowing CKD progression, assessed as the reduction in participant's expected eGFR decline over time.*

4.2.1.1 Main analyses

To evaluate the primary objective a linear mixed effects model will be fitted for each of the primary endpoints. It will be based on the eGFR values obtained at the scheduled visits at and after randomisation (total slope) and at and after 12-week visit (chronic slope) respectively as the dependent variable. The following covariates will be included as fixed effects in the model, in addition to the ones specified [above](#):

- Time (continuous) since randomisation (days)
- Time and treatment interaction
- UACR at randomization

If the model as specified above becomes ill-conditioned or encounters issues with convergence due to too few observations in one of the categories, the corresponding fixed effect will be removed from the model.

In addition, two random effects, intercept and slope corresponding to the time since randomisation, will be incorporated, with an underlying assumption of an unstructured covariance matrix between the two. A covariance matrix that assumes independence between the residuals within each participant but allows for a different standard deviation at each visit, will be applied. Because of that dependence on visit, and due to the early close-down of the study and the ensuing unavailability of late eGFR measurements, only measurements taken up to and including visit 17 (week 69) will be included in the mixed-effects model; however, all available data, including the (quite few) late eGFR measurements beyond visit 17 (week 69), will be summarised descriptively and listed.

The null hypothesis of no difference in slope between SZC and placebo will be tested by considering the fixed effect of time and treatment interaction term in the model. The estimates of the mean slopes obtained from the model, as well as the estimate of the difference between the two slopes, together with two-sided 95% confidence intervals, will be presented. For the difference in slope, the corresponding p-value will also be provided.

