During the study, sites will be notified if the number of participants recruited in a particular cohort approaches a point where further recruitment in the cohort would hinder the achievement of the desired number of participants in the other cohort.

In this study, the randomisation will be stratified by 3 factors: country; inclusion criterion 5 (Section 5.1) categorisation as given above; and SGLT2 inhibitor and/or finerenone use at randomisation.

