### **9.2 Sample Size Determination**

Approximately 3000 participants will be enrolled (screened) to achieve approximately 1500 participants receiving at least one dose of SZC during the initiation phase, consequently leading to a target of 1360 participants randomly assigned to SZC or placebo.

Note that “enrolled” refers to a participant’s, or their legally acceptable representative’s, agreement to participate in the study following completion of the informed consent process.

The assumptions for variability of the eGFR measurements between and within participants used in the calculation below are taken from the DECLARE study (D1693C00001 [NCT01730534]): between-participant SD (ie, SD of the random slopes) of 2.6 and within-participant SD (ie, SD of the residuals) of 7.7. The difference in slopes in the 2 treatment arms is assumed to be 0.75, a magnitude that is deemed clinically relevant. For the purpose of sample size determination, it is also assumed that no acute effects are present, ie, that the decline in eGFR over time in both treatment arms is well-approximated by a single line with a particular slope.

Given this, and assuming a two-sided test of a difference in slopes based on a linear mixed model, with a two-sided significance level of 0.05, is performed, then approximately 1220 participants with complete eGFR data will provide a power of 91% for the evaluation of total slope. This is true provided the following time points for eGFR assessment, in terms of weeks since randomisation, are observed for each participant as a minimum: 0 (randomisation), 6, 12, 16, 20, 24, 46, 69, 92, 96, 100, and 104.

Under the same assumptions (ie, a difference in slopes of 0.75, no acute effect), the power for the chronic slope will be approximately 85%. The evaluation of the chronic slope is assumed to start at 12 weeks.

It is expected that approximately 20% of the eGFR data will be missing. As the eGFR data is correlated within participant, it is assumed that the data points available for a participant will provide information on the missed evaluations, and 20% of missed data would roughly correspond to approximately 10% of randomised participants with no eGFR data available. Hence, 1360 participants will be randomised in the maintenance phase.

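### Covariates enter the two eGFR slope models as main effects only, so the tested time-by-treatment contrast is left essentially unadjusted, at a small cost in precision

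*SAP*

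**What the plan says.** SAP 4.2 (Covariates) gives one list for all model-based analyses: treatment, geographic region, the hyperkalaemia stratum, "Use of SGLT2i/Finerenone at randomisation (yes/no), as indicated by the concomitant-medications collection", and age. For the two slope models, SAP 4.2.1.1 states: "The following covariates will be included as fixed effects in the model, in addition to the ones specified" in that list. The additions are continuous time since randomisation, the time-by-treatment interaction and UACR at randomisation. The null hypothesis is tested on the time-by-treatment term, which is the only interaction in the model. Data are used up to visit 17 (week 69).

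Protocol 6.3.1 says that "the randomisation will be stratified by 3 factors": country, the inclusion-criterion-5 cohort, and SGLT2 inhibitor and/or finerenone use. Age and UACR are not among them, and country reaches the model only as region.

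A factor-by-time term appears in one place, the subgroup homogeneity test in SAP 4.2.1.4, which takes one factor at a time. Protocol 9.4.2.1 leaves covariates beyond time, treatment and their interaction to the SAP.

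**The concern.** A baseline covariate entered as a main effect moves a participant's eGFR level up or down by the same amount at every visit. It says nothing about how fast eGFR falls. The co-primary question is about rate of decline, so the covariate must be crossed with time to take out variation in decline. Without that, any part of the decline that UACR or SGLT2i/finerenone use predicts stays in the random-slope variance and widens the interval for the slope difference.

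The documents treat these factors as relevant to decline. SAP 4.2 gives SGLT2 inhibitors as an example of medication that may affect CKD progression directly, and Protocol 4.2.1 uses albuminuria to select a population at risk of progression. The stakes are precision and calibration. Stratified randomisation balances two of the factors, but the slope comparison does not credit that balance, and a chance imbalance in UACR is not corrected.

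**Working it through.** **Inputs (Protocol 9.2).** The test is run "with a two-sided significance level of 0.05". "The difference in slopes in the 2 treatment arms is assumed to be 0.75", read here as mL/min/1.73m2 per year. Variability: "between-participant SD (ie, SD of the random slopes) of 2.6 and within-participant SD (ie, SD of the residuals) of 7.7". Minimum visits in weeks: "0 (randomisation), 6, 12, 16, 20, 24, 46, 69, 92, 96, 100, and 104". Allocation is 1:1.

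**Step 1: reproduce the stated power.** The per-participant slope variance is 2.6² + 7.7²/Sxx, where Sxx is the sum of squared deviations of visit times in years (weeks/52).
- Total slope: Sxx = 6.755, so the variance is 6.76 + 59.29/6.755 = 15.54. With 610 per arm, SE = √(2 × 15.54/610) = 0.226. Power = Φ(0.75/0.2257 − 1.96) = 91.4%.
- Chronic slope (week 12 onward): Sxx = 4.891, variance 18.88, SE 0.249, power 85.4%.

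The Protocol states that "approximately 1220 participants with complete eGFR data will provide a power of 91% for the evaluation of total slope", and about 85% for the chronic slope. Both reproduce with no covariate gain.

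**Step 2: do main effects change the slope contrast?** In a simulation of 300 trials with N = 1220 on the 104-week grid, three models were compared: no covariate, covariate main effect only, and main effect plus covariate-by-time. Assumptions not taken from the documents are random-intercept SD 10, intercept-slope correlation 0.2, a covariate effect on slope of 1.0 per SD (1/6.76, about 15% of slope variance), and the dropout model.

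| Data | SD, no covariate | SD, main effect | SD, with covariate-by-time |
|---|---|---|---|
| Complete | 0.2127 | 0.2127 | 0.2065 |
| Outcome-dependent dropout, about 10% missing | 0.2519 | 0.2497 | 0.2430 |

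With complete data, the first two estimates were identical in every run. With dropout they correlated 0.999 and differed by at most 0.047; that small adjustment comes through the intercept-slope covariance. The interaction moved individual complete-data estimates by up to 0.17. All means lay close to the true 0.75 (0.747 to 0.758), so bias is not the issue.

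**Step 3: size in the analysis now planned (to week 69).** If the interactions explain a share R² of the slope variance, the variance of the contrast falls by R² × 6.76/(6.76 + 59.29/Sxx). This proportion does not depend on the number randomised. The all-visits rows add weeks 34 and 57 from the Schedule of Activities. R² of 10%-30% is an assumption.

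| Model, visits to week 69 | Sxx | Slope variance | 6.76 as share | Variance fall, R² 10%-30% |
|---|---|---|---|---|
| Total, minimum visits | 1.344 | 50.89 | 13.3% | 1.3%-4.0% |
| Total, all visits | 1.712 | 41.40 | 16.3% | 1.6%-4.9% |
| Chronic, minimum visits | 0.897 | 72.88 | 9.3% | 0.9%-2.8% |
| Chronic, all visits | 1.109 | 60.25 | 11.2% | 1.1%-3.4% |

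In standard-error terms (1 − √(1 − fall)) this is about 0.7%-2.5% for the total slope and 0.5%-1.7% for the chronic slope.

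**Step 4: conservatism.** If all the explained variance came from perfectly balanced factors, the true two-sided level would be 2[1 − Φ(1.96/√(1 − fall))]. Over the week-69 rows this gives 0.0485 to 0.0445 (total) and 0.0489 to 0.0462 (chronic). These are upper limits on the conservatism, since UACR is not balanced by design.

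**The case against.** The strongest reply is that nothing here is invalid. The SAP does what the Protocol allows, randomisation keeps the contrast unbiased, the stated power reproduces without adjustment, and the test errs on the safe side. All of that stands. A reader might infer that the primary result would be biased or that the sample size was miscalculated; the documents support neither.

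A reader might also quote a larger gain. On the 104-week grid the same formula gives 4.3%-13.0% for the total slope, but the current SAP stops at week 69, where residual noise dominates. A smaller residual SD would also raise the figure, but 7.7 is the only value in the documents. Nor should one say that randomisation was stratified on every listed covariate: age and UACR were not, so the chance-imbalance argument has real force mainly for UACR.

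Two further points are fair. The subgroup analyses will show whether decline differs by these factors, though they give no adjusted overall contrast. And extra terms are not entirely free: SAP 4.2.1.1 already foresees convergence trouble, and early closure has thinned the data. These points reduce the importance of the concern without removing it.

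**Conclusion.** The concern holds as a small, inexpensive improvement. As specified, the covariates do almost nothing for either co-primary contrast: exactly nothing with complete, balanced data, and very little with missing data. The loss is about 1.3%-4.9% of variance for the total slope and 0.9%-3.4% for the chronic slope, with a mildly conservative test. The size rests on an assumed R² of 10%-30%, the Protocol's SDs held constant over visits (the SAP lets the residual SD differ by visit), and complete visits to week 69. A reader should not take the slope difference to be covariate-adjusted merely because covariates are listed.

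**What to change.** Before unblinding, make three changes to both slope models in SAP 4.2.1.1:

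- Replace UACR with log(UACR at randomisation) as the main effect, so that the interaction below has its matching main effect. SAP 4.2.4.2 already uses log baseline UACR.
- Add time interactions for the hyperkalaemia stratum, SGLT2i/finerenone use and log(UACR). Centre these covariates so that the reported arm-specific slopes refer to the average participant.
- State that if the fit fails, these interactions are dropped first, before the existing rule on removing fixed effects applies.

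If the data are already unblinded, leave the primary model alone and report this version as a labelled sensitivity analysis. The cost is SAP wording and three interaction terms per model; the downside is a few extra parameters in a data set reduced by early closure.
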